### **9.3. Sample Size Justification**

Because this is an extension study, the sample size will be determined by the number of patients who have completed a parent study and who are eligible and willing to participate in the extension study. It is estimated that approximately 800 patients (67% of the total of 1200 patients who will be randomized into the parent studies) will participate in this study.

### **9.4. Efficacy Analyses**

Unless otherwise specified, efficacy analyses will be conducted using the Extension Study Population.

Efficacy endpoints will be summarized by the original treatment groups assigned in the parent study.

The point estimates and 2-sided 95% confidence intervals (CI) for the primary efficacy endpoints (proportion of responders based on dysmenorrhea NRS scores and use of rescue analgesic medications, proportion of responders based on NMPP scores and use of rescue analgesic medications) will be calculated.

A responder at a given time point and for a specific type of pain (dysmenorrhea or NMPP) is defined as a patient who had a reduction in that type of pain from Baseline in the parent study greater than or equal to a pre-determined threshold and who did not have an increase in the use of rescue analgesic medications for endometriosis-associated pain compared with the use at Baseline. Patients who had a pain reduction less than the pre-determined threshold or who had an increase in the use of analgesics for endometriosis-associated pain will be considered non-responders. The pain reduction thresholds will be determined for NMPP and dysmenorrhea separately (see the SAP for details) for the parent studies and these same thresholds will be applied to this study.

Baseline values are calculated using the Baseline pain assessment period, which is defined as the period from the date of the first dose of placebo in the parent study Run-In Period through the day prior to the first dose of randomized study drug. Patients' average NRS pain scores and use of rescue analgesic medications for endometriosis-associated pain (dysmenorrhea or NMPP) will be compared between a given visit-specific pain assessment period (eg, Week 28, Week 32, etc.) and the Baseline pain assessment period. The visit-specific pain assessment period is defined as the last 35 calendar days immediately prior to and including the last dose of study drug treatment received prior to the visit date.

For any pain assessment period (Baseline or visit-specific), the average NRS scores will be calculated for dysmenorrhea and NMPP separately. An average NRS score for dysmenorrhea is calculated as the average NRS score over the days with menses during a given pain assessment period. An average NRS score for NMPP is calculated as the average NRS score over the days without menses during a given pain assessment period. The analgesic use for a given pain assessment period is summarized by total dose count defined as the average daily dose count taken during the given pain assessment period multiplied by 35. Additional details on calculating dose counts and on the precise definition of an increase in analgesic use will be provided in the SAP.

Descriptive statistics will be provided for efficacy endpoints (listed below) similar to those used for the parent studies at Week 52 and Week 104.

- Change from the parent study Baseline in the EHP-30 Pain Domain scores;
- Change from the parent study Baseline to in the mean dysmenorrhea NRS score;
- Proportion of patients who are better or much better on the PGIC for dysmenorrhea;
- Change from the parent study Baseline in the mean NMPP NRS score;
- Change from the parent Baseline in the mean NRS score;
- Proportion of patients not using opioids;
- Proportion of patients not using analgesics;
- Proportion of patients who are better or much better on the PGIC for NMPP;

- 
- Change from the parent study Baseline in the mean dyspareunia NRS scores;
  - Proportion of patients who are better or much better on the PGIC for dyspareunia;
  - Change from the parent study Baseline in the mean dyspareunia functional impairment on the sB&B scale;
  - Change from the parent study Baseline in severity scores on the PGA for pain;
  - Proportion of responders based on EHP-30 Pain Domain scores;
  - Change from the parent study Baseline in function impairment on the PGA for function;
  - Change from the parent study Baseline in each of the non-pain EHP-30 domains (Control and Powerlessness, Social Support, Emotional Well-Being, and Self-Image);
  - Change from the parent study Baseline pain assessment period in dysmenorrhea-related functional effects (sB&B);
  - Change from the parent study Baseline pain assessment period in NMPP-related functional effects (sB&B).

For binary endpoints, the point estimate and 2-sided 95% CI for the proportion will be provided by parent study treatment group.

For endpoint of proportion of responders based on EHP-30 Pain Domain scores, a responder is defined using the same within-patient score change threshold determined from the parent studies.

Details on the endpoint analyses including derivations, handling of missing data, and statistical methods will be provided in the SAP.

## 9.5. Safety Analyses

Safety assessments will include treatment-emergent adverse events, vital signs and weight, physical examinations, clinical laboratory tests, 12-lead ECG, bone mineral density with DXA, mammograms (for patients required to have this procedure, see Section 6.5.2.9), and endometrial biopsy. Safety summaries by treatment group will be performed using treatment groups defined based on the actual randomized treatment received in the parent study.

The treatment-emergent period will be defined as the period of time from the first dose date and time of randomized study drug in the parent study through 30 days after the last dose of study drug, or the date of initiation of another investigational agent or hormonal therapy affecting the hypothalamic-pituitary-gonadal axis or surgical intervention for endometriosis, whichever occurs first. Safety will be assessed through summaries of adverse events, the frequency of treatment discontinuations due to adverse events, laboratory evaluations, and bone densitometry results.

The severity of all adverse events is to be evaluated by the investigator based on the National Cancer Institute CTCAE. All adverse events will be coded to preferred term, high level term, and system organ class using MedDRA 20.0 or higher. The incidence of adverse events will be presented by MedDRA system organ class and preferred term, relationship to study drug treatment, and severity. A patient reporting the same adverse event more than once is counted

once, and at the maximum severity or strongest relationship to study drug treatment when calculating incidence.

Laboratory data consist of chemistry, hematology, and hormonal tests. Only data collected by the central laboratory will be used to do the analyses. The National Cancer Institute CTCAE will be used to categorize toxicity grade for the laboratory parameters. Shift tables will be provided for each gradable parameter to summarize baseline toxicity grade versus post-baseline toxicity grade. For laboratory parameters that are not gradable by the CTCAE, a shift table based upon the normal range (low, normal, and high) will be provided for each parameter to summarize the parent study Baseline versus post-baseline results. All data will be listed and summarized by visit. The change from parent study Baseline to each post-baseline study visit will be presented by parent study treatment group for each laboratory test.

For vital signs parameters, including temperature, all data will be listed and summarized by visit. The change from parent study Baseline to each post-baseline study visit will be presented by parent study treatment group for each parameter.

Clinical laboratory data consist of chemistry, hematology, and hormonal tests. Only data collected by the central laboratory will be used to do the analyses. Electrocardiograms will also be read centrally. The distributions of QTc interval will be summarized at each visit. All data will be listed and summarized by visit. The change from parent study Baseline to each post-baseline study visit will be presented by treatment group for each ECG parameter.

The incidence of vasomotor symptoms as assessed through adverse event reporting will be summarized by the parent study treatment arm.

Bone mineral density data will be collected and analyzed by the central radiology laboratory including bone mineral content (g), bone area (area, cm^2), and bone mineral density (g/cm^2) each for L1, L2, L3, L4, total hip, and femoral neck, and average bone mineral density of L1-L4 (lumbar spine), Z-score for bone mineral density lumbar spine (L1-L4), total hip, and femoral neck.

For the relugolix add-back treatment Group A, the lower bound of the 95% CI for (arithmetic) mean percentage change at Week 52 from parent study Baseline in bone mineral density lumbar spine (L1-L4) will be compared with a pre-specified clinically acceptable threshold of -2.2% to evaluate magnitude of bone mineral density loss after 52 weeks of treatment. If the lower bound is > -2.2%, the bone mineral density loss for the relugolix add-back treatment will be considered insignificant. As supportive analysis, least square means and 95% CI for percent change at Week 52 from parent study Baseline in bone mineral density will be provided based on mixed effects model (assumed missing at random) for each parent study treatment group. The 95% CI for mean percentage change at Week 104/Early Termination from parent study Baseline in bone mineral density lumbar spine (L1-L4) will be provided along with descriptive statistics for bone mineral density loss at Week 104/Early Termination as supportive analyses.

All data will be listed and summarized by visit. The absolute change and percent change from parent study Baseline to Weeks 36, 52, and 104/Early Termination and associated 95% CIs will be presented by the parent study treatment group for each bone mineral density parameter. The number and percentage of patients meeting a bone mineral density decline of at least 4%, 5%, 6%, or 7% by body area (lumbar spine, total hip, or femoral neck) will be estimated with 95% CIs by the parent study treatment group.

Additional analyses will be performed to examine the correlation between bone mineral density loss with demographic and baseline characteristics and with treatment exposure. Details will be provided in the SAP.

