### **3. STUDY OBJECTIVES AND ENDPOINTS**

Descriptive assessments of long-term efficacy and safety will be made between the parent study Baseline and Week 52, and between the parent study Baseline the end of the extension study (Week 104) for the following parent study treatment groups:

- Parent Study Group A: Randomized to 24 weeks of oral relugolix 40 mg once daily co-administered with 1.0 mg estradiol and 0.5 mg norethindrone acetate in the parent study;
- Parent Study Group B: Randomized to 12 weeks of oral relugolix 40 mg once daily followed by 12 weeks of oral relugolix 40 mg once daily co-administered with 1.0 mg estradiol and 0.5 mg norethindrone acetate in the parent study;
- Parent Study Group C: Randomized to placebo in the parent study.

The parent study Baseline will be used as the reference point for this extension study for all change from baseline-related endpoints. The pain scores during the Baseline Pain Assessment Period of the parent study will establish the patient's baseline for both the parent study and the extension study.

In women with endometriosis-associated pain, the study objectives and corresponding endpoints are as follows:

Objectives	Endpoints
Primary Efficacy	

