## 4. INVESTIGATIONAL PLAN

### 4.1. Overall Study Design

The SPIRIT EXTENSION study is an international phase 3 open-label, single-arm, long-term efficacy and safety study that will enroll eligible patients who have completed their participation in one of the phase 3 randomized, double-blind, placebo-controlled parent studies (MVT-601-3101 or MVT-601-3102). All patients will receive open-label oral relugolix 40 mg once daily co-administered with low-dose estradiol 1.0 mg and norethindrone acetate 0.5 mg for up to 80 weeks. Approximately 800 women with endometriosis-associated pain will be enrolled. The objectives of the study are to evaluate long-term efficacy and safety through up to 104 weeks of treatment (including treatment during the parent study) of relugolix co-administered with low-dose estradiol/norethindrone acetate. Eligible patients will have completed participation in one of the parent studies and consented to participate in this extension study. Baseline procedures will be done at the same visit for this extension study (referred to as the “Week 24/Baseline visit” in this study) that coincides with the Week 24 visit from the parent study and will be defined as the date of completion of the last Week 24 procedure in the parent study. The Week 24/Baseline visit will include vital signs, physical examination, laboratory assessments, a 12-lead electrocardiogram (ECG), bone densitometry, patient-reported outcome assessments, and endometrial biopsy (if required). When Week 24 procedures in the parent study have been completed, the investigator will assess patient eligibility for participation in the open-label extension study. The eligibility assessment will be based on data available at the Week 24/Baseline visit. No MVT-601-3103 study procedures will be performed until the consent form for this extension study is signed.

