Patients will have received their last dose of study drug in the parent study on the day prior to the Week 24/Baseline visit and will receive their first dose of study drug for this extension study in the clinic after the patient is determined to be eligible for this extension study and has provided informed consent to participate. Therefore, results of testing required for eligibility must be available on or prior to the Week 24/Baseline visit. The administration of the first dose of study drug for MVT-601-3103 will define enrollment into this study. Study participants will then take the open-label study treatment (relugolix 40 mg co-administered with estradiol 1.0 mg and norethindrone acetate 0.5 mg) orally once daily for 80 weeks. If necessary for logistical reasons (eg, delayed availability of study drug supply on site, others), and with sponsor/designee approval, the first dose of open-label study drug for MVT-601-3103 may be administered up to 10 days following the parent study Week 24/Baseline visit. If the first dose of study drug is not given during this up to 10-day interval, the parent study follow-up procedures should be followed (ie, adverse event reporting, electronic diary [eDiary] completion, etc.).

During the 80-week Open-Label Treatment Period and the ~30-day Follow-Up Period, patients will continue to record study treatment, assessment of pain using the NRS, menstrual bleeding, analgesic use, and the functional effects of endometriosis-associated pain (sB&B) in the eDiary. Only study-specific rescue analgesic medications should be used starting with the Week 24/Baseline visit and through the Follow-Up visit and these medications will be taken for control of pain and not prophylactically. Health-related quality of life questionnaires; PGIC for dysmenorrhea, NMPP, and dyspareunia; and PGA for pain and function will be completed

during the visits on an electronic tablet or on paper, according to the Schedule of Activities (Section 1.1).

[figure not shown]
Safety will be assessed throughout the study by the monitoring of adverse events, vital signs and weight, physical examinations, clinical laboratory tests, 12-lead ECGs, mammograms (for patients required to have this procedure; see Section 6.5.2.9), endometrial biopsies, and bone mineral density with DXA.

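### For Group C, the treatment-emergent period and the safety baseline start before 24 weeks of placebo, so its Week 52 and Week 104 safety results mix placebo with only 28 or 80 weeks of relugolix plus add-back

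*Protocol*

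**What the plan says.** All references are to the protocol text as amended by Amendment 3.1.

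- **Treatment-emergent period (Section 9.5).** One definition serves all groups: "from the first dose date and time of randomized study drug in the parent study through 30 days after the last dose". An earlier listed event, such as starting another hormonal therapy, ends the period sooner.
- **Group C (Section 3).** "Parent Study Group C: Randomized to placebo in the parent study".
- **Reference value (Section 3).** "The parent study Baseline will be used as the reference point for this extension study for all change from baseline-related endpoints". Section 9.5 repeats this for laboratory tests ("The change from parent study Baseline to each post-baseline study visit will be presented by parent study treatment group for each laboratory test"), vital signs and ECG, and for BMD ("absolute change and percent change from parent study Baseline to Weeks 36, 52, and 104/Early Termination").
- **Grouping (Section 9.5).** "Safety summaries by treatment group will be performed using treatment groups defined based on the actual randomized treatment received in the parent study".
- **Counting rule (Section 9.5).** A patient with repeated occurrences of an event counts once, at the greatest severity or strongest relationship.
- **Duration (Section 4.1).** Open-label drug is taken "orally once daily for 80 weeks", and the stated aim is to "evaluate long-term efficacy and safety through up to 104 weeks of treatment (including treatment during the parent study) of relugolix" with add-back.
- **BMD decision rule (Section 9.5).** The lower 95% confidence bound for lumbar spine change at Week 52 is compared with -2.2% in Group A only.

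**The concern.** The safety objective in Section 3 is the safety of relugolix with add-back for up to 104 weeks. In Groups A and B, time since the first parent dose is time on relugolix. In Group C it is not, yet the same start date and the same baseline apply, and the protocol defines no on-relugolix period for that group.

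Three results are affected:

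- **Adverse events.** A woman with headache on placebo and again on relugolix appears once, so the incidence table cannot show under which treatment an event arose. Section 7.10 lists hot flush, headache and hyperhidrosis as identified relugolix risks, so this matters for the events of most interest.
- **Laboratory shifts.** The starting grade precedes the placebo phase. If the shift is to any post-baseline grade (Section 9.5), placebo-phase values count directly. If it is visit by visit (Synopsis), a Week 52 shift still spans 24 weeks of placebo and 28 weeks of drug.
- **BMD.** Group C's Week 52 change stands beside Group A's with the same visit label but about half the drug exposure. A reader comparing the columns could take shorter exposure for better bone safety.

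**Working it through.** **The plan's own horizon.** 24 parent weeks + 80 open-label weeks = 104 weeks, as stated. For Group C only the 80 are on relugolix.

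**Group C time on each treatment** (nominal visit weeks)

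| Report | Placebo weeks | Relugolix weeks | Placebo share |
|---|---|---|---|
| Week 52 | 24 | 52 - 24 = 28 | 24/52 = 46.2% |
| Week 104 | 24 | 104 - 24 = 80 | 24/104 = 23.1% |

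With a full 30-day tail the shares are 168/(364 + 30) = 42.6% and 168/(728 + 30) = 22.2%. The placebo share in Groups A and B is 0%.

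**Adverse event incidence (illustration).** The protocol gives no event rates, so 24-week risks on placebo (p) and relugolix (a) are assumed, with constant hazards. For a report at week T:

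- relugolix time only: 1 - (1 - a)^((T - 24)/24)
- protocol definition: 1 - (1 - p)(1 - a)^((T - 24)/24)

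| Assumed p / a | Week 52: relugolix only | Week 52: protocol | Week 104: relugolix only | Week 104: protocol |
|---|---|---|---|---|
| 10% / 30% | 34.0% | 40.6% | 69.5% | 72.6% |
| 30% / 50% | 55.5% | 68.8% | 90.1% | 93.1% |
| 50% / 50% | 55.5% | 77.7% | 90.1% | 95.0% |

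The protocol figure is higher by about 7 to 22 percentage points at Week 52 and 3 to 5 at Week 104. Adding placebo time adds patients with events. In the 30%/50% case, 52 weeks entirely on relugolix would give 1 - 0.5^(52/24) = 77.7%, so 68.8% describes neither 28 nor 52 weeks of drug.

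**BMD (illustration).** Assume a linear loss of 1% per 52 weeks on drug and a placebo-phase change d.

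- Group A at Week 52: -1.0%.
- Group C at Week 52 from parent Baseline: d - 28/52 = -0.54% if d = 0. It is -0.84% to -0.24% for d from -0.3% to +0.3%.
- Group C at Week 52 from the Week 24 value: about -0.54% whatever d is.
- At Week 104 with d = 0: Group C -80/52 = -1.54%, Group A -2.0%.

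Most of the gap between Groups A and C is therefore exposure time. The choice of baseline moves Group C's BMD result only by d.

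**Can the data be split?** Yes. The Schedule of Activities has DXA, laboratory tests, vital signs and ECG at Week 24/Baseline. Its adverse event footnote assigns events with onset before the first extension dose to the parent study, and Section 7.2.1 starts extension collection at that dose.

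**The case against.** A reader might infer more than this: that placebo experience is reported as long-term relugolix safety, or that it dilutes the BMD and laboratory results. The documents do not support either.

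- Every safety summary is by parent group, and Group C is identified as the placebo group. No combined A, B and C estimate is specified. A pooled table with equal thirds (an assumption) would carry 24/(3 × 52) = 15.4% and 24/(3 × 104) = 7.7% placebo time, but none is planned.
- The only BMD decision rule uses Group A, and the supportive mixed-model estimates are given for each parent group.
- For adverse event incidence the direction is inflation, the opposite of dilution.
- Section 4.2 attributes the roughly one-year data to women first randomized to relugolix, which leaves out Group C.
- The Schedule of Activities states that visit timing is relative to the parent studies, so Week 52 names a visit. The Synopsis summarizes drug exposure separately, and Section 9.5 plans to relate BMD loss to exposure.
- The Week 24 values are not discarded. BMD is summarized by visit including Week 24/Baseline, and Group C's parent Baseline is itself drug-free.

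All of this stands, and it confines the problem to Group C. It is also fair that Section 9.2 lets the SAP specify otherwise, so an on-relugolix table may be planned there. It does not remove the rule that Section 9.5 states: one start date for everyone, and one count per patient per event. Grouping by parent arm labels the column correctly but does not separate the two treatments inside it.

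**Conclusion.** The point holds for Group C only. Under the stated rules its adverse event incidence and laboratory shifts are mixed-treatment results, with placebo making up 46% of nominal on-study time at Week 52 and 23% at Week 104. Its BMD changes at those visits reflect at most 28 and 80 weeks of drug. Neither can be read as 52 or 104 weeks of relugolix plus add-back. Groups A and B and the comparison of Group A with -2.2% are unaffected.

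The time shares rest only on the protocol's visit weeks. The 7 to 22 and 3 to 5 point differences in incidence, and the BMD figures, rest on assumed rates and show direction and rough size only.

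A related contradiction needs settling. The Synopsis takes safety data from all parent-study patients given any study drug, while Section 9.2 limits the Safety Population to patients dosed in the extension. Read literally, the Synopsis would place in Group C women who received placebo and never took relugolix.

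This is worth changing. It does not threaten the main BMD conclusion.

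**What to change.** Keep the parent-group, parent-Baseline tables, which give all three groups a common time scale. Add for Group C in Section 9.5 (or the SAP, if not already there):

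1. Treatment-emergent time starting at the first open-label dose, with placebo-period adverse events in a separate column.
2. The Week 24/Baseline value, the last before the first relugolix dose, as reference for BMD, laboratory, vital sign and ECG changes.
3. Exposure labelled as 28 weeks (Week 52 visit) and 80 weeks (Week 104 visit) on relugolix plus add-back.

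Leave the pain endpoints on the parent Baseline. Make the Synopsis safety paragraph and Section 9.2 name the same safety data set.

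The cost is some protocol or SAP wording and a few extra tables; no new measurements are needed. The downside is a second time scale for Group C, so the added tables must be clearly headed as weeks on relugolix plus add-back.

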### **Inclusion/Exclusion Criteria**

**Inclusion Criteria:** A woman will be eligible for enrollment in this study only if all of the following inclusion criteria apply and have been met at the time of the Week 24/Baseline visit:

1. Completed 24 weeks of study drug treatment and study participation in either MVT-601-3101 or MVT-601-3102;
2. Has voluntarily signed and dated the informed consent form prior to initiation of any study-specific procedures for MVT-601-3103;  
Note: Procedures conducted as part of the parent study that also serve as baseline procedures for this study will be done under the informed consent for the parent study.
3. Is not expected to undergo gynecological surgery or other surgical procedures for treatment of endometriosis (including ablation, shaving, or excision) during the study, including during the Follow-Up Period, and the patient does not desire such treatment during this time frame;
4. Has a negative urine pregnancy test at the Week 24/Baseline visit;
5. Has agreed to continue to use only study-specified analgesic medications during the study and is not known to be intolerant to these;
6. Agrees to continue to use acceptable non-hormonal contraceptive methods as described in Section 4.6 consistently during the Open-Label Treatment Period and for at least 30 days after the last dose of study drug. However, the patient is not required to use the specified non-hormonal contraceptive methods if she:
  - a. Has a sexual partner(s) who was vasectomized at least 6 months prior to the Week 24/Baseline visit;
  - b. Had a bilateral tubal occlusion (including ligation and blockage methods such as Essure™), at least 6 months prior to the Week 24/Baseline visit (patients with Essure must have prior confirmation of tubal occlusion by hysterosalpingogram) and there must be no evidence of post-Essure syndrome;
  - c. Has a non-hormonal intrauterine device (eg, Paragard®) placed in the uterus;
  - d. Is not sexually active with men; periodic sexual relationship(s) with men requires the use of non-hormonal contraception as noted above;
  - e. Practices total abstinence from sexual intercourse, as her preferred lifestyle; periodic abstinence is not acceptable.

**Exclusion Criteria:** None of the following criteria may be true for a patient to be eligible for enrollment into this study.

1. Has had a surgical procedure for treatment of endometriosis at any time during the parent study (MVT-601-3101 or MVT-601-3102);

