### Safety

Safety assessments will include treatment-emergent adverse events, vital signs and weight, physical examinations, clinical laboratory tests, 12-lead ECG, bone mineral density with DXA scan, mammograms (for patients required to have this procedure, see Section 6.5.2.9), and endometrial biopsy. Safety data analyses will use data from all patients from the parent studies who receive any amount of study drug (ie, from parent study Baseline to Week 52 or Week 104).

Drug exposure will be summarized by descriptive statistics. Severity of all treatment-emergent adverse events will be evaluated by the investigator based on the National Cancer Institute Common Terminology Criteria for Adverse Events (CTCAE) and will be coded to preferred term, high level term, and system organ class using the Medical Dictionary for Regulatory Activities (MedDRA). The number and percentage of patients with adverse events will be presented by MedDRA system organ class and preferred term, relationship to study drug, and severity. Laboratory values will be classified by toxicity grade based on the National Cancer Institute CTCAE. Laboratory shift tables of the parent study Baseline results to each of the subsequent visits will be produced.

Bone mineral density will be evaluated in all patients at the lumbar spine (L1-L4), femoral neck, and total hip at the Week 24/Baseline, Week 36, Week 52, and Week 104/Early Termination visits. The absolute change and percent change from parent study Baseline and Z-scores will be summarized by visit and parent study treatment group.

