## **9. STATISTICAL CONSIDERATIONS AND DATA ANALYSES**

A statistical analysis plan (SAP) will describe the detailed statistical methods and analyses for this study.

All efficacy and safety measures over the course of both the parent and extension studies will be presented by the parent study treatment group using descriptive statistics. No formal treatment comparisons will be performed for this extension study. Continuous data will be summarized by means, standard deviations, medians, maximum, minimum, and number of patients. Categorical data will be summarized by counts and percentages.

There will be two analyses: one at Week 52 and one at Week 104. A clinical study report will be generated from each analysis.

The study may be closed pending selected contingent safety procedures conducted after the last patient's Week 104/Early Termination or Follow-Up visit. After the study is closed, any pending required follow-up testing of bone mineral density and endometrial biopsies or for menstruation recovery beyond the Follow-Up visit will be captured and reported.

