### **9.2. Analysis Populations**

Efficacy data analyses will be performed on the Extension Study Population, defined as all patients who enrolled into MVT-601-3103 and who have received any amount of randomized open-label study drug in MVT-601-3103.

Safety data analyses will be performed on the Safety Population, defined as all enrolled patients who have received any amount of MVT-601-3103 study drug.

The analysis methods for safety and efficacy endpoints are the same as those used for the parent studies, unless otherwise specified in the SAP.

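### Adverse events are summarised as crude percentages over follow-up of about 24 to 104 weeks; a sound description, but not a 104-week risk, and person-time and cumulative-incidence summaries should sit beside it

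*Protocol*

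**What the plan says.** The safety endpoint is the incidence of adverse events, assessed at Week 52 and Week 104, under an objective of safety for up to 104 weeks (Sections 1 and 3).

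- **Statistic.** Section 9.5: "The incidence of adverse events will be presented by MedDRA system organ class and preferred term, relationship to study drug treatment, and severity". The synopsis is more explicit: "The number and percentage of patients with adverse events will be presented by MedDRA system organ class and preferred term". Section 9 sets the general rule: "Categorical data will be summarized by counts and percentages".
- **Counting.** Section 9.5 says "A patient reporting the same adverse event more than once is counted" only once.
- **Window.** It opens at the first randomised dose in the parent study and runs "through 30 days after the last dose of study drug". It closes earlier if certain other therapies or endometriosis surgery intervene. Each woman therefore has her own follow-up time.
- **Denominator.** Section 9.2 uses a Safety Population "defined as all enrolled patients who have received any amount of MVT-601-3103 study drug". The synopsis instead says "Safety data analyses will use data from all patients from the parent studies who receive any amount of study drug".
- **Entry.** Inclusion criterion 1 requires that a woman has "Completed 24 weeks of study drug treatment and study participation in either MVT-601-3101 or MVT-601-3102".

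Drug exposure is summarised on its own. No person-time rate or time-to-event estimate is attached to adverse events, and none is ruled out. Section 9 leaves detailed methods to the SAP, and Section 9.2 carries over the parent-study methods unless the SAP says otherwise.

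**The concern.** A crude percentage gives a woman followed for 30 weeks the same weight as one followed for 104. Under the Section 9.2 definition, follow-up can differ by up to 80 weeks, so the percentage is neither a rate nor, in general, a cumulative risk at a fixed time. The 24-week parent studies, whose safety methods carry over by default, had a much shorter planned period in which follow-up could differ.

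At stake is how the Week 104 report will be read. A figure labelled incidence at Week 104, under an objective of safety up to 104 weeks, is easily taken as the chance of the event over two years. For events that arise late, that reading would be too favourable. The gap would also be wider in the Week 104 report than in the Week 52 report, so the two percentages would not be directly comparable.

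**Working it through.** **The protocol's own figures.** 800/1200 = 66.7%, stated as 67%. Parent treatment of 24 weeks plus 80 extension weeks gives 104. Both reproduce. No adverse event rate, extension dropout rate or power is stated, so the risk R and dropout d below are assumptions.

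**Model for Week 104.** R is the true risk over 104 weeks plus 30 days (30/7 = 4.29 weeks), 108.29 weeks in all. A fraction d leaves, unrelated to adverse event risk and spread evenly over Weeks 24 to 104. Each leaver is observed for 30 more days.

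- Constant hazard: h = −ln(1 − R)/108.29. For R = 10%, h = 0.10536/108.29 = 0.000973 per week, about 5.1 per 100 patient-years.
- Mean risk observed among leavers: m = 1 − [exp(−28.29h) − exp(−108.29h)]/(80h) = 6.4%.
- Crude percentage = (1 − d)R + d·m.

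Results for R = 10%:

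| Pattern | d = 20% | d = 35% | d = 50% |
|---|---|---|---|
| Constant hazard: crude percentage | 9.3% | 8.7% | 8.2% |
| relative shortfall | 7% | 13% | 18% |
| Events only after Week 52: crude percentage | 8.7% | 7.8% | 6.8% |
| relative shortfall | 13% | 23% | 32% |
| Events only before Week 24: shortfall | 0% | 0% | 0% |
| Extreme, all leavers at Week 24, constant hazard: crude percentage | 8.5% | 7.5% | 6.4% |
| relative shortfall | 15% | 26% | 36% |

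Worked line for d = 20%, constant hazard: 0.8 × 10 + 0.2 × 6.4 = 9.28%, a shortfall of 0.72 points. For events only after Week 52, the hazard is 0.10536/(108.29 − 52) = 0.00187 per week and m = 3.6%. The relative shortfall under constant hazard hardly depends on R: at 20-50% dropout it is 7-18% for R = 2% and 7-17% for R = 30%.

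**Week 52 against Week 104.** For this comparison the 30-day tail is left out at both times. With h = 0.10536/104 = 0.001013 per week, the true Week 52 risk is 1 − √0.9 = 5.13%. Only 28/80 = 35% of the leavers go before Week 52.

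| Dropout by Week 104 | Shortfall at Week 52 | Shortfall at Week 104 |
|---|---|---|
| 20% | 1.9% | 7.5% |
| 50% | 4.6% | 18.7% |

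Under these same assumptions a person-time rate or a Kaplan-Meier estimate would recover the assumed hazard or risk.

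**The case against.** The strongest reply is that this is a matter for the SAP. Section 9 sends detailed methods there, the SAP is not shown, and nothing in the protocol bars exposure-adjusted rates. That stands as far as omission goes: the absence of such rates from the protocol is not shown to be an error. It does not dispose of the point, because the synopsis and Section 9.5 positively choose the patient percentage. Section 9.5 also goes into method for bone density, where it names a mixed model under missing at random, but makes no allowance for unequal follow-up in adverse events.

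Three further replies stand and limit the point:

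- The analysis is descriptive, the objective says up to 104 weeks, and no decision rule rests on an adverse event percentage.
- Women removed under Section 4.5 because of a liver, endometrial or bone finding have the finding before they leave. If it is recorded as an adverse event it is already counted, and removal does not uncount it. Only departure before the event of interest matters.
- Early Termination brings an endometrial biopsy and, at or after Week 36, a DXA scan, each with stated exceptions. Serious events reported after the window still go to the sponsor. Ascertainment at exit is therefore better than a bare dropout model implies.

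A reader might infer that dropout by itself lowers a two-year risk that the trial reports. The documents do not support that. The protocol never calls the percentage a two-year risk. The direction and size of any shortfall depend on when events arise and on whether leaving is related to them.

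**Conclusion.** The crude percentage is acceptable as a description and should stay; reading it as 104-week risk is what must be avoided. With departure unrelated to the event, dropout of 20-50% and constant hazard, it falls short of the cumulative risk by about 7-18% in relative terms, or 0.7 to 1.8 percentage points at a true 10%. The range runs from nil for events before Week 24 to about 32% for events arising only after Week 52 with 50% dropout. The shortfall is larger at Week 104 than at Week 52. If leaving is related to adverse event risk, the bias can differ from these figures.

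The 24-week minimum rests on Section 9.2. The synopsis draws on all dosed parent-study patients, which would allow shorter follow-up; the two definitions need to be reconciled. This is a worthwhile improvement to reporting, not an error that invalidates the safety analysis.

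**What to change.** In Section 9.5, or in the SAP with a pointer from Section 9.5:

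1. Keep the number and percentage of patients, and state that they are not estimates of risk at Week 52 or Week 104.
2. Add, by system organ class and preferred term, first events per 100 patient-years at risk.
3. For a short prespecified list (for example fracture, thromboembolic, hepatic and vasomotor events, and discontinuation due to adverse events), add cumulative incidence at Weeks 52 and 104 with 95% CIs. Treat discontinuation because of another adverse event as a competing event, or examine it in a sensitivity analysis.
4. Use one Safety Population definition in the synopsis and Section 9.2.

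The cost is a few extra tables from dosing and event dates already recorded. The additions have limits that should be stated: rates per patient-year assume a roughly constant hazard, and cumulative incidence assumes that dropout is non-informative.
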